#### 5.5.4.2 Dose Modifications

### 5.5.4.2.1 Dose Treatment Delays due to Toxicity or Progression

Subjects who experience blinded investigational product-related toxicity during a cycle must have recovered as specified above before the next cycle may proceed. Any dose modifications except those indicated as mandatory below (including dose delay, reduction, resumption, and discontinuation) are to be performed at the discretion of the Investigator. Further guidelines suggesting dose modifications based on prior studies of rovalpituzumab tesirine are provided in Section 5.5.4.2.2, Dose Reduction Guidelines.

[figure not shown]
In cases of treatment delays of > 28 days, the TA MD should be contacted regarding the subject's continuation of treatment.

In the event of isolated CNS-only progression during study treatment, blinded investigational product will be withheld while local treatment is administered (e.g., radiotherapy) in accordance with institutional practice. Blinded investigational product may be restarted 1 week after the completion of local CNS disease-directed therapy. If more than 6 weeks have elapsed since the previous radiographic tumor assessment, the subject must undergo a radiographic tumor assessment to evaluate extracranial disease status prior to resuming blinded treatment. If additional sites of PD are present, the subject will be required to discontinue blinded investigational product.

#### 5.5.4.2.2 Dose Reduction Guidelines

Blinded investigational product dose reductions and discontinuation of blinded investigational product for specific toxicities should occur as outlined in Table 4, Dose Reductions for Blinded Investigational Product (IP) and Table 5, Dose Reductions and Discontinuation for Unacceptable Toxicities. Dose reductions for unacceptable toxicities described in Table 5 are mandatory. Reduced dose levels are described in (Table 4). Generally, if unacceptable toxicity recurs after two dose reductions, treatment will be discontinued (for further details, refer to Table 5). If the blinded investigational product dose is reduced, no re-escalation will be allowed. If different unacceptable toxicities occur in sequential treatment cycles (e.g., Grade 3 LFT after the first dose and Grade 3 thrombocytopenia lasting more than 7 days after the second dose), dose reduction will proceed to the next lower dose level. If different unacceptable toxicities occur within one cycle, maximum specified dose reduction will be implemented. Dose reductions and discontinuation are not planned for dexamethasone/placebo. If full dose of dexamethasone/placebo cannot be administered due to an AE, the blinded infusion should be delayed until dexamethasone/placebo can be administered.

Exceptions to the dose modification guidelines should be discussed with the TA MD prior to implementation.

Details of toxicity management are further outlined in Section 6.1.8, Toxicity Management.

Table 4. Dose Reductions for Blinded Investigational Product (IP)

Starting Dose	First Dose Reduction (Reduce Dose)	Second Dose Reduction (Reduce Dose)
0.3 mg/kg	0.2 mg/kg	0.1 mg/kg

[figure not shown]

Table 5. Dose Reductions and Discontinuation for Unacceptable Toxicities

Toxicity a	First Occurrence	Second Occurrence
Grade 3 thrombocytopenia lasting more than 7 days	Reduce dose to 0.2 mg/kg	Reduce dose to 0.1 mg/kg
Grade 4 thrombocytopenia/Grade 3 thrombocytopenia with bleeding/Need for platelet transfusion	Reduce dose to 0.1.mg/kg	Discontinue Blinded IP
Grade 4 neutropenia lasting more than 7 days	Reduce dose to 0.2 mg/kg	Reduce dose to 0.1 mg/kg
Grade 3 febrile neutropenia	Reduce dose to 0.2 mg/kg	Reduce dose to 0.1 mg/kg
Grade 4 febrile neutropenia	Reduce dose to 0.1.mg/kg	Discontinue Blinded IP
Grade 3 Liver Function Tests (LFTs)	Reduce dose to 0.2 mg/kg	Reduce dose to 0.1 mg/kg
Grade 4 LFTs or Grade 3 LFTs with concomitant Bilirubin Grade 2 or higher b	Reduce dose to 0.1.mg/kg	Discontinue Blinded IP
Potential DILI (Drug-induced liver injury)	See Section 6.1.8.3	See Section 6.1.8.3
Grade 3 or 4 hypoalbuminemia	Reduce dose to 0.1 mg/kg	Discontinue Blinded IP
Any other Grade 3 or 4 laboratory abnormality considered clinically significant and treatment-related	Reduce dose to 0.2 mg/kg	Reduce dose to 0.1 mg/kg
Grade 2 serosal effusions or edema	Reduce to 0.2 mg/kg	Reduce to 0.1 mg/kg
Grade 3 serosal effusions or edema or Grade 2 capillary leak syndrome	Reduce dose to 0.1.mg/kg	Discontinue Blinded IP
Grade 4 serosal effusions or edema or Grade ≥ 3 capillary leak syndrome	Discontinue Blinded IP	N/A
Grade 3 photosensitivity reaction	Reduce dose to 0.2 mg/kg See Section 6.1.8.2	Reduce dose to 0.1 mg/kg See Section 6.1.8.2
Grade 4 photosensitivity reaction	Discontinue Blinded IP	N/A
Grade 2 pneumonitis	Reduce dose to 0.1 mg/kg	Discontinue Rova-T
Grade ≥ 3 pneumonitis	Discontinue Rova-T	N/A
Any other Grade 3 or Grade 4 non-laboratory treatment-related toxicity with the exception of fatigue, asthenia, nausea, or other manageable constitutional symptom	Reduce dose to 0.2 mg/kg	Reduce dose to 0.1 mg/kg

a. Refer to Appendix H, CTCAE v 4.0 Grading of Relevant AEs for definitions of NCI-CTCAE severity grades and for definition of serosal effusions and edema.

b. If potential DILI is suspected please follow guidelines of Section 6.1.8.3.

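### For a subject cut straight from 0.3 to 0.1 mg/kg who then has another Table 5 toxicity, the mandatory dose instructions in Protocol 5.5.4.2.2 conflict

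*Protocol*

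**What the plan says.** All of the relevant text is in Protocol Section 5.5.4.2.2.

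- Status: "Dose reductions for unacceptable toxicities described in Table 5 are mandatory". Sections 5.5.4.2.1 and 6.1.8 are consistent with this: both set the mandatory modifications apart from those left to the investigator.
- Dose levels: Table 4 runs from 0.3 to 0.2 to 0.1 mg/kg. It labels 0.2 as the first reduction and 0.1 as the second, and lists nothing lower.
- Table 5: each row gives an absolute dose, or discontinuation, for a first and for a second occurrence. The row "Grade 2 serosal effusions or edema" goes to 0.2 and then 0.1 mg/kg. The row "Grade 3 serosal effusions or edema or Grade 2 capillary leak syndrome" goes to 0.1 mg/kg and then discontinuation.
- Different toxicities in sequential cycles: "dose reduction will proceed to the next lower dose level".
- Different toxicities in the same cycle: "If different unacceptable toxicities occur within one cycle, maximum specified dose reduction will be implemented".
- Re-escalation: "If the blinded investigational product dose is reduced, no re-escalation will be allowed".
- Stopping: "Generally, if unacceptable toxicity recurs after two dose reductions, treatment will be discontinued", with a pointer to Table 5 for details.
- Exceptions are to be discussed with the sponsor's medical director before they are implemented.

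**The concern.** The table works by counting occurrences of each toxicity and naming a fixed dose. The text works relative to the subject's current dose. The two agree while the subject steps down one level at a time. They need not agree after a direct cut to the lowest level, because a first occurrence of a new toxicity can then name a dose above the current one, and there is no lower level to move to.

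The subjects concerned have already had one of the more severe listed toxicities, and the instructions are mandatory. Sites could reasonably reach different answers. Those answers would feed into dosing, into the exposure and dose-intensity summaries of SAP Section 9.0, and into the counts in SAP Section 11.2 of adverse events leading to reduction or discontinuation.

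**Working it through.** No power or alpha figure is involved. The check applies each table entry to each possible current dose.

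**Inputs.** Table 5 has 18 rows. One (potential drug-induced liver injury) only refers to Section 6.1.8.3, which leaves 17 dosing rows. By first-occurrence entry:

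- 0.2 mg/kg, eight rows: prolonged Grade 3 thrombocytopenia, prolonged Grade 4 neutropenia, Grade 3 febrile neutropenia, Grade 3 liver tests, other Grade 3–4 laboratory abnormality, Grade 2 effusion or edema, Grade 3 photosensitivity, other Grade 3–4 non-laboratory toxicity.
- 0.1 mg/kg (direct cut), six rows: Grade 4 thrombocytopenia or its equivalents, Grade 4 febrile neutropenia, Grade 4 liver tests or Grade 3 with raised bilirubin, Grade 3–4 hypoalbuminemia, Grade 3 effusion or edema (with Grade 2 capillary leak), Grade 2 pneumonitis.
- Discontinue, three rows: Grade 4 effusion or edema (with Grade 3 or higher capillary leak), Grade 4 photosensitivity, Grade 3 or higher pneumonitis.

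8 + 6 + 3 = 17.

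**First-occurrence entry compared with current dose (number of rows):**

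| Current dose | Lower | Same | Higher | Discontinue |
|---|---|---|---|---|
| 0.3 mg/kg | 14 | 0 | 0 | 3 |
| 0.2 mg/kg | 6 | 8 | 0 | 3 |
| 0.1 mg/kg | 0 | 6 | 8 | 3 |

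For a subject who reached 0.1 mg/kg by a direct cut, remove the row that caused it. That leaves 8 higher, 6 − 1 = 5 same and 3 discontinue, 16 rows in all. In 8 + 5 = 13 of the 16, the entry is not a reduction that can be made.

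**What the text adds.** At 0.2 mg/kg, the eight same-dose entries are resolved for sequential cycles, because the next level down is 0.1. The section's own example is of this kind: a Grade 3 liver-test event takes the subject to 0.2 mg/kg, and prolonged Grade 3 thrombocytopenia then has a level to move to. At 0.1 mg/kg the same sentence points to a level that Table 4 does not have.

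**One subject traced.** A Grade 3 effusion after the first dose leads to 0.1 mg/kg. Prolonged Grade 3 thrombocytopenia follows after the second dose.

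1. Table 5 entry: 0.2 mg/kg.
2. Re-escalation sentence: bars 0.2 mg/kg.
3. Sequential-toxicity sentence: a level below 0.1 mg/kg, which does not exist.
4. Discontinuation sentence: its result depends on two points that the text leaves open.

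| Direct cut counts as | New toxicity counts as a recurrence | New toxicity does not count |
|---|---|---|
| Two reductions (Table 4 label) | Generally discontinue | Sentence not triggered |
| One reduction (one step taken) | Sentence not triggered | Sentence not triggered |

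**Grades of one toxicity.** Take the Grade 3 effusion at 0.1 mg/kg followed by a Grade 2 effusion. Counted within grade, it is a first occurrence in the Grade 2 row (0.2 mg/kg, barred). Counted as one effusion series, it is a second occurrence, which is 0.1 mg/kg in the Grade 2 row. In the reverse order, a Grade 2 then a Grade 3 effusion gives 0.1 mg/kg if counted within grade, and discontinuation if counted as one series and read in the Grade 3 row.

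**The case against.** The best defence is that a careful reader can find a way through. The 0.2 mg/kg entries are worded as reductions and re-escalation is barred, so no one would take them as an order to increase. For sequential cycles the text has its own sentence, so the raw table entry need not govern. The stopping sentence speaks of unacceptable toxicity in general and not of the same toxicity. Since Table 4 labels 0.1 mg/kg the second reduction, a subject there can be read as having had two. Section 6.1.8.2 counts a second Grade 3 photosensitivity reaction within its grade, which suggests how occurrences are meant to be counted. There are also backstops: exceptions go to the medical director, Section 5.4 lets the investigator stop treatment at any time, and Section 5.5.4.1 withholds dosing until related events resolve. The path is narrow as well: a direct-cut event, recovery, a dose at 0.1 mg/kg, then another listed event.

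Much of this stands, and it rules out three stronger readings.

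- A reader might infer that the protocol tells these subjects to take a higher dose. It does not: the re-escalation sentence makes this a conflict between table and text.
- A reader might infer that the Table 5 doses fit only a subject at 0.3 mg/kg. They do not: the six direct-cut entries and the whole second-occurrence column work from 0.2 mg/kg, and the discontinue entries work from any dose.
- A reader might infer that there is no stop rule at 0.1 mg/kg. There is one for a repeat of the same direct-cut row and for the three discontinue rows, and the general sentence may supply one elsewhere.

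What the defence does not do is close the gap. The reading that resolves it needs two counting conventions that Section 5.5.4.2.2 does not state. The photosensitivity wording is one example and not a general rule. An exceptions route and investigator discretion do not say what the mandatory rule is.

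**Conclusion.** The conflict is real but limited to subjects who reached 0.1 mg/kg by a direct cut and then have a first occurrence in another row. For them, 8 of the 16 other rows name a barred dose, 5 name the current dose and 3 discontinue. The sequential-toxicity sentence has no level to move to, and the discontinuation sentence applies only on a reading that the text neither states nor excludes.

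These counts describe the table, not patients. It is tempting to gauge frequency from the adverse-event rates in Protocol Section 3.5 (for example pleural effusion 33.9%, edema 33.8%) or by multiplying rows together. The Section 3.5 rates are given without grade, Section 6.1.8.4 says that most edema was Grade 1 or 2, and no rate is given for direct-cut events or for a second event at 0.1 mg/kg. The number of subjects affected is therefore unknown, and no effect on the PFS or OS analyses is shown. The case for correction is that mandatory safety instructions should not contradict each other when followed as written. No view is taken on which dose or rule is right.

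**What to change.** Reconcile Table 4, Table 5 and the re-escalation, sequential-toxicity and discontinuation sentences of Section 5.5.4.2.2, so that together they give one consistent instruction for a subject already at 0.1 mg/kg. In the same edit, make clear:

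- whether a direct cut from 0.3 to 0.1 mg/kg counts as one reduction or two;
- whether a different toxicity counts as a recurrence for the discontinuation sentence;
- whether different grades of the same toxicity are counted as one series of occurrences or separately.

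The clinical team decides the content and the form of the rule. The cost is rewording one paragraph and its tables in the next amendment, with no new data or procedures.

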#### 5.5.5 **Blinding**

#### 5.5.5.1 **Blinding of Investigational Product**

AbbVie, the Investigator, the study site personnel, and subject will remain blinded to each subject's treatment with royalpituzumab tesirine or placebo and dexamethasone or placebo and throughout the course of the study.

The IRT system will provide access to blinded subject treatment information during the study. AbbVie must then be notified within 24 hours of the blind being broken. The date and reason that the blind was broken must be recorded in the source documentation and eCRF, as applicable.

[figure not shown]
#### 5.5.5.2 Blinding of Data for Independent Data Monitoring Committee (IDMC)

An Independent Data Monitoring Committee (IDMC) will be formed and constituted according to appropriate regulatory guidelines. The IDMC will review the unblinded data from the study with respect to subject accrual, pretreatment characteristics of accrued subjects, the frequency and severity of toxicities and morbidity, and provide recommendations according to the charter. Detailed information regarding the composition of the committee and procedures including frequency of meetings and scope of reviews will be documented in a separate charter. For the futility analysis, OS, other efficacy and safety data will be analyzed and reviewed by the IDMC for recommendation.

#### 5.5.6 **Treatment Compliance**

The investigator or his/her designated and qualified representatives will administer/dispense blinded investigational product only to subjects randomized in the study in accordance with the protocol. The blinded investigational product must not be used for reasons other than that described in the protocol.

Blinded investigational product administration must be performed by study site staff and documented in source documents and the eCRF.

[figure not shown]
# 5.5.7 Drug Accountability

The site will record the dose of rovalpituzimab tesirine/placebo and dexamethasone/placebo given to each subject in the source documents and on the eCRF.

Upon receipt of a shipment of rovalpituzimab tesirine/placebo and dexamethasone/placebo, the representative at each site will (1) open and inspect the shipment; (2) verify that the rovalpituzimab tesirine/placebo has been received intact, in the correct amounts and at the correct address; (3) sign and date the Proof of Receipt (POR) or similar documentation accompanying the shipment; (4) register the shipment as received via the IRT. All blinded investigational products must be retained in the designated secure area under proper storage conditions. This will be documented by signing and dating the Proof of Receipt (POR) or similar document or via direct recording in the IRT.

An overall accountability of the blinded investigational product will be performed and verified by the site monitor throughout the study and at the study site closeout visit. An accurate running inventory of rovalpituzimab tesirine/placebo and dexamethasone/placebo will be maintained utilizing the IRT drug accountability module and, if required, according to your institutional policy and will include the lot number, POR number(s), the bottle/kit numbers, and the date blinded investigational product was dispensed for each subject.

Upon completion or termination of the study, all original bottles/cartons containing unused rovalpituzimab tesirine/placebo and dexamethasone/placebo (empty containers will be defaced and discarded on site) will be returned to the Destruction Facility according to AbbVie's instructions, or if pre-arranged between the sponsor and site, destruction of used and unused bottles will be performed at the site. Rova-T is classified as a Dangerous Good/Hazardous Material according to US Department of Transportation (DOT) and International Air Transport Association (IATA). Dangerous Goods/Hazardous Materials must be packaged and shipped according to applicable regulations.

The study Investigator or his/her designated representative agrees not to supply study medication to any persons not enrolled in the study or not named as a sub-investigator listed on the FDA 1572 or Investigator Information and Agreement (IIA) form.

## 5.6 Discussion and Justification of Study Design

# 5.6.1 Discussion of Study Design and Choice of Control Groups

Phase 1 data described in Section 3.0 and proposed mechanism of action suggest that rovalpituzumab tesirine may improve outcome of SCLC patients by extending clinical benefit following first-line platinum-based chemotherapy. This randomized, double-blind, placebo controlled phase 3 study will evaluate the effect of rovalpituzumab tesirine as maintenance therapy following first-line platinum-based chemotherapy of extensive stage SCLC. Primary endpoints of PFS and OS are well established in solid tumor trials and in SCLC specifically.

[figure not shown]
A randomized, double-blind, placebo controlled study such as described here is optimal for assessing the treatment effect of rovalpituzumab tesirine versus current standard, best supportive care to a current standard treatment (placebo is required to allow for blinding).

## 5.6.2 Appropriateness of Measurements

The safety measures that will be used in this trial are considered standard procedures for evaluating the potential adverse effects of study medications. Adverse events and, when applicable, clinical laboratory data will be graded using NCI CTCAE, version 4.0.

Response will be assessed according to RECIST v1.1, which includes standard criteria for evaluating response in solid tumors. The intervals of evaluation in this protocol are appropriate for disease management.

Standard tests will be performed to detect the possible presence of specific antibodies to blinded investigational product. Pharmacokinetic assessments for drug activity are also common in clinical studies.

## 5.6.3 Suitability of Subject Population

[figure not shown]
Although response rates to first-line chemotherapy remain high with platinum-based regimens, time to disease recurrence is short in extensive-stage SCLC. Rovalpituzumab tesirine has demonstrated anti-tumor activity in relapsed/refractory SCLC population. Exploring rovalpituzumab tesirine in ED SCLC subjects with stable disease or objective response following first-line chemotherapy is acceptable considering observed activity/toxicity profile of rovalpituzumab tesirine, and that the standard approach in this setting is no treatment until progression.

## 5.6.4 Selection of Doses in the Study

In a recent Phase 1 study (SCRX16-001) with rovalpituzumab tesirine, the maximum tolerated dose (MTD) was established at 0.4 mg/kg every 3 weeks based on the incidence of Cycle 1 toxicities, while the recommended Phase 2 dose (RPTD) in SCLC was chosen as 0.3 mg/kg every 6 weeks for a total of two doses with the allowance to retreat at the same dose level and schedule upon progression. The RPTD is based on the toxicity and efficacy profile during multiple cycles dosing (AbbVie Stemcentrx data on file). This experience included multiple doses of rovalpituzumab tesirine at a) 0.2 mg/kg every 6 weeks, b) 0.3 mg/kg every 6 weeks or c) 0.3 mg/kg every 6 weeks for a total of two doses and then at 0.1 mg/kg every 6 weeks thereafter. Based on the totality of the experience with rovalpituzumab tesirine and taking into consideration its pharmacokinetic characteristics, dosing of 0.3 mg/kg q6wk for 2 cycles, omitting every third cycle will be used in this study. This study will not exceed a maximum dose of 1.5 mg/kg at each dose.

# 6.0 Complaints

A complaint is any written, electronic, or oral communication that alleges deficiencies related to the physical characteristics, identity, quality, purity, potency, durability, reliability, safety, effectiveness, or performance of a product/device after it is released for distribution.

The investigational product in this study is defined as rovalpituzumab tesirine or placebo and dexamethasone or placebo. Complaints associated with any component of this investigational product must be reported to the Sponsor (Section 6.2.2). For AEs, please refer to Sections 6.1.1 through 6.1.6. For product complaints, please refer to Section 6.2.

# 6.1 Medical Complaints

The investigator will monitor each subject for clinical and laboratory evidence of adverse events on a routine basis throughout the study. The investigator will assess and record any adverse event in detail including the date of onset, event diagnosis (if known) or sign/symptom, severity, time course (end date, ongoing, intermittent), relationship of the adverse event to blinded investigational product, and any action(s) taken. For serious adverse events considered as having "no reasonable possibility" of being associated with blinded investigational product, the investigator will provide an Other cause of the event. For adverse events to be considered intermittent, the events must be of similar nature and severity. Adverse events, whether in response to a query, observed by site personnel, or reported spontaneously by the subject will be recorded.

All adverse events will be followed to a satisfactory conclusion.

### 6.1.1 Definitions

### 6.1.1.1 Adverse Event

An adverse event (AE) is defined as any untoward medical occurrence in a patient or clinical investigation subject administered a pharmaceutical product and which does not necessarily have a causal relationship with this treatment. An adverse event can therefore be any unfavorable and unintended sign (including an abnormal laboratory finding), symptom, or disease temporally associated with the use of a medicinal (investigational) product, whether or not the event is considered causally related to the use of the product.

Such an event can result from use of the drug as stipulated in the protocol or labeling, as well as from accidental or intentional overdose, drug abuse, or drug withdrawal. Any worsening of a pre-existing condition or illness is considered an adverse event.

Rovalpituzumab Tesirine M16-298 Protocol Amendment 4 EudraCT 2016-003503-64

Worsening in severity of a reported adverse event should be reported as a new adverse event. Laboratory abnormalities and changes in vital signs are considered to be adverse events only if they result in discontinuation from the study, necessitate therapeutic medical intervention, meets protocol specific criteria (see Section 6.1.8 regarding toxicity management) and/or if the investigator considers them to be adverse events.

An elective surgery/procedure scheduled to occur during a study will not be considered an adverse event if the surgery/procedure is being performed for a pre-existing condition and the surgery/procedure has been pre planned prior to study entry. However, if the pre-existing condition deteriorates unexpectedly during the study (e.g., surgery performed earlier than planned), then the deterioration of the condition for which the elective surgery/procedure is being done will be considered an adverse event.

All protocol-related AEs must be collected from the signing of the study specific informed consent until study drug administration.

In addition, adverse events with onset or worsening reported by a subject from the time that the first dose of study drug is administered until 70 days have elapsed following discontinuation of study drug administration will be considered as treatment-emergent adverse events.

